Potential mechanisms for the effect of BNO on symptoms and subjective balance have been proposed, including stabilizing one's sense of orientation by providing a "visual anchor", improving the ability to filter out irrelevant visual information and suppress visual motion, increasing the use of ambient vision, and improving visual attention by reducing the integration of information between the two central visual fields (Ciuffreda, Yadav, & Ludlam, 2017; Gallop, 2014; Padula, Capo-Aponte, Padula, Singman, & Jenness, 2017). Visual attention in the visual cortex using visual-evoked potentials (VEP) has been shown to be impaired post-concussion (Yadav et al., 2014). Thus, improvements in visual attention and stability with BNO may allow an individual to allocate more attention to postural control. Evidence of this would be seen as improved balance during visually-based cognitive dual-task conditions.

High quality studies in the field of vision therapy in the management of concussion are lacking, as research has been limited to case studies and extrapolations from other pathologies (Ciuffreda, Yadav, & Ludlam, 2013; Ciuffreda et al., 2017; Gallop, 1998, 2014; Proctor, 2009). These studies suffer from methodological limitations such as lack of randomization and comparison groups, small sample sizes, and lack

of standardized protocols. While some of these studies did report an immediate and significant improvement in subjective symptoms and functional balance during gait, objective measures of postural sway and oculomotor function were not investigated.

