Studies have compared single- with dual-task performance on COP post-concussion, (Degani et al., 2017) or the presence of saccadic dysfunction post-concussion, using visually-based cognitive dual-tasks (Rizzo et al., 2016; Subotic et al., 2017). However, to date, no study has directly compared the effect BNO as an intervention on measures of COP velocity, objective metrics of saccadic eye movement, and symptoms during the performance of single- and visually-based cognitive dual-task balance conditions in a concussion population. This makes it difficult for clinicians to make evidence-informed choices in the management of individuals who experience persistent balance deficits beyond the expected period of normal recovery following a concussion. This study aims to address this gap by assessing the efficacy of a BNO intervention trial in adults with persistent post-concussion balance problems compared with a control condition using both single and visually-based cognitive dual-task balance paradigms. The study is designed as a randomized controlled crossover test with a sample size calculated a priori to ensure the contribution of high quality evidence to a nascent body of literature.

OBJECTIVES

Purpose

The overarching research question is the following: What is the effect of BNO compared with no binasal occlusion on measures of static balance, saccadic eye movement functions, and symptoms in adults who continue to experience dizziness one month or longer following a concussion? The specific objectives of this study are (1) to measure the effect of BNO on postural sway, compared with non-occluded vision during quiet stance on a force plate; (2) to examine the impact of BNO on postural sway while performing a visually based cognitive dual-task compared with target-focused vision, as measured during quiet stance on a force plate; (3) to compare the effect of BNO on saccadic eye function, compared with non-occluded vision during a timed reading task. Saccadic eye function will be quantified as time to completion during the KDT and the total number of saccades; (4) to determine the relationship between a rapid number naming task and observable saccadic eye function; (5) measure the association between self-reported symptoms, disability, and objective measures of balance in adults who continue to experience dizziness longer than one month after concussion.

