It is hypothesized that BNO will improve postural sway during a visually based cognitive dual-task more than during quiet stance. We also hypothesize that time to completion of a timed reading task will correlate positively with saccadic eye function, and that both will show improvement with BNO. It is further hypothesized that perceived disability due to dizziness and neck pain would be greater in

individuals with increased postural sway. This article presents the research protocol for this study.

METHODS

Design

This cross-sectional study will examine the effect of BNO on balance in adults aged 18-65 years who continue to experience symptoms one month or more following a concussion. A 2-task, 2-period, 2 treatment condition randomized crossover study design will be used in order to be balanced with respect to first-order effects, as each condition will precede the other condition only once. Potential participants will be screened for eligibility during a telephone interview. Following enrollment, they will be randomized to one of two condition sequences and act as their own control group. Participants will perform two different balance tasks repeated under both treatment (BNO) and control (no BNO) conditions. The treatment/control conditions will be the same for each participant with only the order of each treatment/control sequence randomized. Post-concussion syndrome is considered chronic and stable, and thus suitable for a crossover study design. Likewise, the application of BNO is intended to improve immediate functional balance and saccadic eye movement, rather than cure the concussion. No evidence of the effect time of BNO has been reported in the literature. Based on clinical experience of two of the authors, the treatment effect is limited to the time of application, so there should be no carryover effect between conditions and a negligible washout period between trials is considered sufficient. To minimize any risk of potential carryover effects, patients will also be asked to wait the greater of 1 minute, or until all symptoms return to their pre-test baseline before performing the subsequent task. A summary of the study design is available in Figure 1. All study procedures will be conducted at one of two private rehabilitation clinics in Ottawa, Canada.

Participants

Patient selection

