During a telephone screening interview, potential participants will speak with a member of the research team to confirm study eligibility, to review details of the study protocol, and to enroll in the study if deemed suitable. During this discussion, potential participants will be given the opportunity to request an electronic copy of the informed consent form to review prior to meeting with the study team. Once enrolled, participants will attend an in-person testing session at one of the two trial locations. At this session, the research team will review: (1) the purpose of the study; (2) how the randomization process works; (3) a general overview of the testing conditions, and the self-report outcome measures. A thorough discussion of potential risks and benefits associated with participation in the study will then take place, as well as the assurance that participants may withdraw from the study or request a rest at any time during the study without consequence or without effect on the medical care that they receive. Each participant will be given a hard copy of

the informed consent form for signature and an extra copy to take home. Participants will be given as much time as required to re-read and complete the informed consent form, as well as the opportunity to ask for and receive clarification for questions as necessary.

Sample size

40 participants will be recruited for the present study. A power analysis based on COP excursion using a force plate with adults following a concussion has been calculated to determine the number of participants that need to be recruited for the present study. A change in COP excursion by more than 5cm will be considered to be significant, as this represents the minimal detectable change with a 90% confidence interval (Goble, Manyak, Abdenour, Rauh, & Bawega, 2016). A two-tailed analysis will be made with alpha level set at 0.05 and power set at 80%. Due to the nature of this crossover design, loss to follow-up is not expected, and therefore not accounted for in the sample size determination.

Randomization

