Participants will be randomly assigned to one of two groups for a crossover study design. Each group will complete both arms of the study, randomized to sequence, starting with either the control condition or the intervention condition. The intervention condition consists of performing the identical balance tasks while wearing glasses overlaid with BNO. Researchers performing the intervention will not be blinded to group allocation due to the crossover design.

OUTCOME MEASURES

For each arm of the study, participants will complete two trials of static balance while standing on a force plate that will record movement of the center of pressure (COP) under their feet. Sensors from an electromagnetic tracking system will also be attached to each participant at the base of the skull, T5, and L5 along the spine, collecting acceleration of movements, angular velocity of movements, and angular rotation of the earth. The sensors will record accelerations of movements, angular velocities, and angular rotations. Throughout each trial condition, Tobii™ eye tracker glasses will be worn to measure and record saccadic eye movements and time to task completion.

Primary outcome

Balance – COP

Measurement of postural sway as an indicator of persistent balance impairment post-concussion builds upon previous studies demonstrating increased postural sway in the acute period following a concussion (Goble et al., 2016). The primary outcome of interest is the mean M/L and A/P velocity of COP, in addition to the 95% ellipse during different conditions of static balance. The minimal clinical difference

considered to demonstrate a change in postural sway is 5cm based on a previous validation study in a concussed population (Goble et al., 2016).

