For balance task B, participants will be asked to stand shoulder width apart on the BTS with their hands on their hips. Participants will be asked to complete a cognitive task while they maintain their balance. The visually based cognitive dual-task will involve the participants performing the King-Devick Test (KDT). Test cards will be fixed to a wall and positioned 12 inches from the participant's face at eye level. Participants will be asked to read the numbers out loud as quickly and as accurately as possible, from left to right, beginning at the top left corner of each test card. The total time to read all 3 test cards and the total number of errors committed will be recorded. If a participant makes an error, they will be asked to restart the test. The test usually takes less than two minutes to complete. Participants who complete the KDT in less than 2 minutes will be asked to restart the test from the beginning and continue reading for the remainder of the test period. Those individuals who require more than the allotted 2 minutes to complete the KDT will continue with the rapid number naming task until completion, and COP data will stop being collected at 2 min.

Throughout each trial, participants will be fitted with a pair of Tobii™ eye tracking glasses that will record their eye movements.

Control condition: normal vision

During the control arm of the trials, the eye tracking glasses will remain unobstructed and vision will not be occluded.

Experimental intervention: BNO

During the intervention arm of the trials, strips of occlusive material will be placed on the medial portion of each lens of the Tobii[™] eye tracking glasses to occlude central integrated vision.

Planned statistical analyses

Baseline characteristics for participants will be compared with descriptive statistics (mean, SD, n, %).

The primary objective, the effect of BNO on postural sway, will be addressed by using a dependent t-test to compare differences between treatment conditions for each COP variable. A similar analysis using a dependent t-test (group^xKDT_{time to} completion) will be performed to assess the secondary objective, the effect of BNO on reading. Additionally, a Wilcoxon Signed Rank test will be used to determine if there is a significant difference in the number of saccades completed on the KDT between

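### The primary paired t-test does not say which balance task's BNO-minus-control difference decides the trial, and no listed analysis tests the hypothesised difference between tasks

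*Protocol*

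**What the plan says.** The Design and Balance Testing Protocol sections have every participant do both tasks under both conditions. Each COP variable therefore yields two BNO-minus-control differences per person, one in task A and one in task B.

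Planned statistical analyses gives the primary test in one sentence, whose operative part reads: "will be addressed by using a dependent t-test to compare differences between treatment conditions for each COP variable". That sentence names no task, and there is no rule for averaging, ordering or combining tasks.

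The other places that could settle it do not:

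- **Primary outcome (Balance – COP):** two COP velocities are named, and a third measure is added with the phrase "in addition to the 95% ellipse during different conditions of static balance". Table 2 lists COP measures without a task.
- **Sample size:** this section sets 40 participants, a two-sided alpha of 0.05 and 80% power, and takes 5 cm of COP excursion as the change of interest. There is one alpha, no split, and no task.
- **Objectives:** the first item reads "1) to measure the effect of BNO on postural sway, compared with non-occluded vision during quiet stance on a force plate", whereas the second concerns the dual task set against target-focused vision.
- **Hypotheses (end of Objectives):** the stated expectation is "BNO will improve postural sway during a visually based cognitive dual-task more than during quiet stance".
- **Introduction, on the attention mechanism:** here the text says "Evidence of this would be seen as improved balance during visually-based cognitive dual-task conditions".

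**The concern.** The contrast that decides the trial is not fixed. For any one COP variable, the text admits a primary test in task A, in task B, or on some combination of the two. The Protocol itself expects the tasks to respond to different degrees, so the candidates need not agree. Followed literally, the plan gives two primary verdicts per COP variable at a single unsplit 0.05.

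Two things are at stake. If a significant result in either task may be called a positive primary result, the error rate is above the stated 5%. Separately, the one hypothesis that compares the tasks has no test: neither per-task t-test addresses whether BNO helps more in the dual task than in quiet stance.

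This is distinct from the three COP variables being primary together. It would remain if only one of them were kept, and the two problems multiply.

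**Working it through.** **Inputs from the Protocol.** n = 40, each under both conditions; two-sided alpha 0.05; power 80%; 5 cm change in COP excursion; 2 tasks; 3 primary COP variables. **Not given:** the SD of the paired difference, the correlation between the two tasks' differences, and the effect in either task. These are assumed below, over ranges.

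**1. The plan's own figure.** N = 40 cannot be reproduced without an SD. Back-solving a paired t-test (noncentral t, 39 df) for 80% power at n = 40 gives a standardised difference of 0.454, so the implied SD of the difference is 5 / 0.454 ≈ 11.0 cm. The normal approximation gives (1.960 + 0.842) / √40 = 0.443, or 11.3 cm. Nothing says whether such an SD would belong to task A or task B.

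**2. One COP variable, either task may count.** With independent tasks the false-positive rate is 1 − 0.95² = 9.75%. Simulation (40,000 null trials, n = 40, paired t-test in each task) gives:

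| Between-task correlation (assumed) | P(at least one task significant) |
|---|---|
| 0 | 9.9% |
| 0.3 | 9.4% |
| 0.5 | 9.2% |
| 0.8 | 7.8% |

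The simulation standard error is about √(0.09 × 0.91 / 40,000) = 0.14 percentage points.

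**3. Two tasks by three COP variables.** With six independent tests, 1 − 0.95⁶ = 26.5%. Under three assumed sets of positive correlation between tasks and between variables (0.3 and 0.5; 0.5 and 0.7; 0.8 and 0.8), simulation gives 23%, 19% and 15%.

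**4. How often the tasks would disagree (illustration only).** Set the task B effect at 0.454, so that task B alone has 80% power, and vary the correlation from 0 to 0.8:

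- No effect in task A: opposite significance verdicts in 77% to 79% of trials. Check at correlation 0: 0.80 × 0.95 + 0.20 × 0.05 = 0.77.
- Half the effect in task A: 52% to 63%.
- Equal effects: 15% to 32%.

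**5. The untested hypothesis.** With equal SDs in the two tasks, the paired comparison (task B difference minus task A difference) has standardised effect (d_B − d_A) / √(2 − 2r). At n = 40:

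| Assumed effects | r = 0 | r = 0.3 | r = 0.5 | r = 0.8 |
|---|---|---|---|---|
| d_B = 0.454, d_A = 0 | 51% | 66% | 80% | 99% |
| d_B = 0.454, d_A = 0.227 | 17% | 22% | 29% | 60% |

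The comparison can be made from the planned data, but its power depends heavily on quantities that the Protocol does not give.

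**The case against.** **The text does point somewhere.** Planned statistical analyses describes the primary objective in nearly the words of objective 1, and the dual task is a separate objective. One natural reading is therefore that task A is primary. But the term for quiet stance is used loosely: the Abstract can be read as applying it to both tasks, and objective 2 also ends with it. Objective 1 could thus cover both. This weakens any claim that objective 1 means task A alone, and it leaves the deciding contrast no more definite.

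**The hypothesis does not contradict objective 1.** This stands. A reader might infer that the two are opposed, or that the hypothesis makes the dual task the deciding test. It does neither. It is a comparison of effect sizes between tasks and is compatible with an effect in quiet stance. The Introduction also lists mechanisms, such as a visual anchor and the suppression of visual motion, that are not specific to a dual task.

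**Some of this belongs in a statistical analysis plan.** Gatekeeping detail often does, and that plan may exist. But this Protocol itself states the primary objective, test, alpha and sample size, and which contrast those refer to is part of that statement.

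**The disagreement rates are assumption-driven.** This stands. They rest on assumed effects. Where BNO works only in the dual task, disagreement is mostly the correct result. They show that the choice of task matters; they do not measure harm.

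**A reader might infer that both tasks' differences would be stacked** into one t-test as 80 independent values. Nothing in the Protocol says so. It specifies a dependent t-test between conditions within 40 participants.

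**Conclusion.** The point holds as an unfixed primary contrast. The primary test, the primary outcome and the sample size name no task, each participant supplies a difference in both tasks, and the only hypothesis that compares the tasks has no analysis. It does not hold as a contradiction between objective 1 and the hypothesis.

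The firm size is the either-task error rate: about 8% to 10% against 5% for one COP variable, over assumed between-task correlations of 0.8 down to 0. With all three COP variables it is 26.5% under independence, and about 15% to 23% under the correlations tried. These rates apply if any significant result may be called a positive primary result; the Protocol does not say that it may, but it states nothing to prevent it. The sponsor should correct this before analysis.

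**What to change.** In Planned statistical analyses, before any data are analysed:

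1. State one deciding task contrast, with one difference per participant per task (n = 40), tested at two-sided 0.05. Test the other task at 0.05 only if the first is significant. Task B first fits the Introduction's attention argument and the hypothesis. If the sponsor holds objective 1 to be primary, task A goes first and the hypothesis text is aligned.
2. Name the single COP variable to which this gate applies, or the multiplicity rule over the three. Task order alone does not hold 5%: three variables at 0.05 in the first task still allow 1 − 0.95³ = 14.3% if independent. At the standardised effect of 0.454, Bonferroni over three variables (0.0167 each) gives 64.5% power, against 80% for one named variable.
3. Add the within-person comparison of the BNO effect between tasks (task B difference minus task A difference, paired t-test) as the named secondary test of the hypothesis.
4. Say which task the power statement refers to only if its SD comes from that task. The 5 cm excursion figure is not tied to either task and should not be assigned to one without support.

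The cost is a few sentences, with no change to testing or sample size. The downside is that the second task can no longer carry a positive primary conclusion on its own. Splitting alpha equally (0.025 per task) for one COP variable would avoid this, but lowers power at 0.454 from 80% to 70.5%.

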Title: The Effect of Binasal Occlusion on Balance Following a Concussion: a Randomized Controlled Trial Protocol

NCT number: not available

Document Date: November 16, 2017

THE EFFECT OF BINASAL OCCLUSION ON BALANCE FOLLOWING A CONCUSSION: A RANDOMIZED CONTROLLED TRIAL PROTOCOL

ABSTRACT

Introduction

While most individuals will recover within the first month after concussion, a significant number will continue to experience dizziness, balance problems, cognitive deficits, and vision problems. Single-task measures of static balance may not be sensitive enough to capture mild postural changes still associated with incomplete recovery. Increasingly there is an interest in dual-task paradigms of balance assessment as a more accurate representation of functional postural control associated with activities of daily living and sport participation. Binasal occlusion (BNO) has been proposed as a means of providing visual stabilization to improve postural control in individuals with vision-related balance problems following a concussion. The purpose of this study is to assess the efficacy of BNO during the performance of both single and dual-task conditions in adults who continue to experience dizziness one month or longer following a concussion. It is hypothesized that BNO will improve balance and saccadic eye function, and reduce symptoms. This article presents the research protocol for this study.

Methods and analysis

This study is a randomized crossover design balanced with respect to first-order effects. Participants will be recruited and randomly assigned to one of two treatment sequences, binasal occlusion (BNO) or non-occluded vision. Both groups will perform the same static balance tasks, including quiet stance performed during target-focused vision and a visually based cognitive dual-task. Following a short washout period, participants will repeat the balance tasks under the alternate treatment condition. The primary outcome measure is centre of pressure (COP) velocity in both the medial-lateral (M/L) and anterior-posterior (A/P) planes and 95% ellipse. Secondary outcome measures include saccadic eye function and self-report measures of symptoms and disability (neck and dizziness related). **Ethics and dissemination:**

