A force to the head or body that results in a concussion is of sufficient force to injure the soft tissue and joints of the cervical spine. Altered proprioception from injured cervical spine structures can contribute to symptoms of dizziness commonly associated with concussion. The NDI is the most commonly used self-report outcome measure for neck pain (MacDermid et al., 2009). The index is a simple and quickly administered 10-item questionnaire measured on a 6-point Likert scale from 0=no disability to 5 = full disability. Scores range from 0-50, with 50 representing the highest level of disability. Psychometric properties of scores demonstrate highly stable test-retest reliability (r=0.94-0.95) in patients with neck pain longer than 3 weeks (MacDermid et al., 2009). Clinically important difference have been reported with a 5-7 point change in score depending on whether the pain was of musculoskeletal or neural origin (MacDermid et al., 2009).

Saccadic eye function

Saccadic eye function will be assessed with two measures, a Tobii[™] Pro wearable eye tracker and the KDT. Tobii[™] Pro wearable eye tracker uses infrared videooculography to analyze patterns of eye movement in terms of fixations and saccades (www.tobiipro.com). Longer, more complicated visual tasks, such as rapid number naming, require longer processing times. The number of saccades completed during each balance condition will be recorded by the Tobii[™] Pro. The KDT is a vision-based test of rapid number naming speed that acts as a proxy measure for saccadic eye movement (Galetta, Liu, et al., 2015). The KDT consists of a demonstration card, plus a series of 3 increasingly more difficult test cards of variably spaced single digit numbers (Subotic et al., 2017). Following completion of the demonstration card, participants are asked to read each test card from left to right, top to bottom, as quickly as possible without errors. A summary score of the test is recorded as the total time to complete all 3 test cards, measured in seconds. Time to completion for the KDT will be recorded by the TobiiTM Pro. A meta-analysis demonstrated high test-retest reliability (ICC=0.92; CI_{95%}: 0.91, 0.94) in baseline trials (Galetta, Liu, et al., 2015).

Domain	Measure	Outcome of Interest		
		Baseline Disability	Primary	Secondary
Cervical spine	Neck Disability Index	Х		
Dizziness	Dizziness Handicap Inventory	Х		
Postural sway	M/L COP excursion		Х	
	A/P COP excursion		Х	
	95% ellipse COP		Х	

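### Three unranked COP measures are primary, each with its own t-test, and the protocol does not say which of them, or what combination, answers its single primary objective

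*Protocol*

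**What the plan says.** - **Abstract, Methods and analysis.** The primary outcome is COP "velocity in both the medial-lateral (M/L) and anterior-posterior (A/P) planes and 95% ellipse".
- **Outcome measures, Primary outcome.** The wording here is "The primary outcome of interest is the mean M/L and A/P velocity of COP, in addition to the 95% ellipse during different conditions". No order of importance is given.
- **Table 2.** Three rows are ticked as primary: "M/L COP excursion", "A/P COP excursion" and "95% ellipse COP". The table says excursion where the text says velocity, but the count is three in both.
- **Planned statistical analyses.** There is one primary objective: "The primary objective, the effect of BNO on postural sway, will be addressed". The method given for it is a separate test per measure: "by using a dependent t-test to compare differences between treatment conditions for each COP variable".
- **Sample size.** A two-tailed alpha of 0.05 and 80% power are set for a power analysis on COP excursion, with no direction named, leading to 40 participants. No other significance level appears in the protocol.

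The protocol does not rank the three measures, combine them, adjust for them, or say how many must succeed.

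**The concern.** The objective is one statement about one construct, sway, but three separate tests are planned to answer it. When they disagree, for example a significant ellipse with null M/L and A/P results, the protocol does not say whether BNO has been shown to affect sway. The authors could then choose the lead measure with the results in hand. If a single significant measure were reported as an effect of BNO on balance, the 5% error rate would not describe that conclusion. The protocol says the results will inform clinicians' decisions on managing balance problems after concussion, so the basis for a positive conclusion should be clear before the data are seen.

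**Working it through.** **Inputs from the protocol.** Three primary measures (Abstract; Primary outcome; Table 2); a paired t-test for each (Planned statistical analyses); two-tailed 0.05, 80% power and N = 40 in a crossover (Sample size).

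**Inputs assumed.** Any one p<0.05 counts as success; 0.05 applies to each test; no true effect on any measure; correlations among the three within-person differences. The protocol gives no correlations, so a range is shown.

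**The plan's own figure.** The protocol states no error rate for the three tests together, so there is none to reproduce. N = 40 cannot be reproduced either, because no SD of the within-person difference is given.

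**Step 1: independent tests.**
- Either direction: 1 − 0.95³ = 1 − 0.857 = 0.143.
- In BNO's favour (nominal 0.025): 1 − 0.975³ = 1 − 0.927 = 0.073.

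**Step 2: correlated tests.** Simulation of three one-sample t-tests on paired differences, n = 40, 39 df, critical value 2.023, 400,000 replicates per row.

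| Assumed correlation | At least one, either direction | At least one in BNO's favour | All three significant |
|---|---|---|---|
| 0 | 14.2% | 7.3% | under 0.1% |
| 0.5 | 12.6% | 6.3% | 0.3% |
| 0.8 | 9.9% | 4.9% | 1.4% |
| 0.9 | 8.4% | 4.2% | 2.2% |
| 0.95 | 7.4% | 3.7% | 3.0% |
| M/L with A/P 0.3, ellipse with each 0.7 | 11.7% | 5.9% | 0.4% |
| M/L with A/P 0.5, ellipse with each 0.8 | 10.7% | 5.3% | 0.8% |

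All three measures come from the same plate and the same trial, so zero correlation is the least plausible row. The last two rows are a more realistic pattern, because the ellipse reflects sway in both directions.

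**Step 3: the same tests under other rules.**
- All three required (last column): 3% or less when no measure has a true effect, at every correlation shown.
- Holm, first step at 0.05/3 = 0.0167: 4.9% at correlation 0, falling to 2.7% at 0.95.

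**Step 4: the power cost of Holm.** No SD is needed if the protocol's own 80% is taken as true. With 40 pairs and two-sided 0.05, 80% power corresponds to a standardised paired difference of 0.454 (noncentral t). At that effect, power is 65% at 0.0167 and 70% at Holm's second threshold of 0.025. At the last threshold of 0.05 it returns to 80%. Restoring 80% at 0.0167 would take 54 participants.

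**The case against.** The strongest case against is that success rules and multiplicity adjustment are commonly left to a statistical analysis plan. One may exist here, so the absence of an adjustment is not in itself a fault of the protocol. That stands. What remains is that the protocol itself states the primary tests, gives three measures equal primary status, and ties all three to one objective.

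Two stronger readings are tempting, and the protocol supports neither.

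- **A reader might infer that the trial runs a false-positive risk of up to 14%.** That needs a rule that any one significant result is enough, which the protocol nowhere states, together with zero correlation, the least plausible case. If all three must succeed, or if each measure is reported only as its own claim, the inflation does not arise.
- **A reader might infer that the protocol assigns a full 0.05 to each of the three tests.** The 0.05 appears only in the sample-size paragraph, for COP excursion. The analysis section gives no significance level.

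It may also be said that the protocol has a second bar, the 5 cm change. That figure is stated for COP excursion. It cannot be applied directly to a velocity or an ellipse area, and it is not described as a joint criterion with the t-tests, so it does not settle which measure leads.

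**Conclusion.** The point holds as a gap in what the protocol fixes: three equal primary measures, three tests, one objective, and no statement of which result or combination answers it. The choice of headline measure is therefore open after the results are known.

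The error rates are a conditional illustration, not a property of the plan as written. They assume that any one p<0.05 counts, 40 participants, no true effect, and correlations that the protocol does not give. On those assumptions the chance of at least one false positive is about 10.7% to 11.7% at plausible unequal correlations, within a range of 7.4% to 14.2%. In the hypothesised direction it is 3.7% to 7.3%, against 2.5%. Confidence is medium, because the success rule is assumed and an analysis plan that is not shown could supply one. The change should be made, but the trial does not fail without it.

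**What to change.** Before any outcome data are examined, do one of the following.

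1. **Preferred: one lead measure.** Name one COP measure as the single primary test at two-sided 0.05, and state which task it uses or that the tasks are pooled. Make the other two secondary, reported as estimates with 95% confidence intervals. State how the lead measure relates to the COP excursion behind N = 40, and restate the sample-size basis if it does not correspond.
2. **Alternative: keep all three as primary with Holm.** If N = 40 truly gives 80% power for one test at 0.05, power at the first step is about 65% per measure, somewhat better after a first rejection. The stated 80% would have to be restated.

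If the intention is that all three must succeed, saying so also holds 5%. The cost is power: with 80% for each measure, the chance that all three succeed runs from 0.8³ = 51% if independent to 80% if perfectly correlated.

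Option 1 is a text change in the Abstract, the Primary outcome section, Table 2 and Planned statistical analyses, plus the Sample size paragraph if the lead measure is not the excursion used there. Its cost is that the conclusion can no longer rest on whichever measure turns out positive. A lead measure in a single task also leaves the hypothesis of a larger effect in the dual-task than in quiet stance to be tested as its own contrast.
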